#### Management Guidelines for Immune-Mediated Myocarditis

Event	Management
Immune-mediated myocarditis, Grade 1 (CTCAE v4.0 guidelines only)	CTCAE v4.0 guidelines 
 
• Refer patient to cardiologist.
 
• Initiate treatment as per institutional guidelines.
 

Immune-mediated myocarditis, Grade 2	
 
• Withhold atezolizumab for up to 12 weeks after event onseta and contact Study Chair.
 
• Refer patient to cardiologist.
 
• Initiate treatment as per institutional guidelines and consider antiarrhythmic drugs, temporary pacemaker, ECMO, or VAD as appropriate.
 
• Consider treatment with corticosteroids equivalent to 1-2 mg/kg/day IV methylprednisolone and convert to 1-2 mg/kg/day oral prednisone or equivalent upon improvement.
 
• If event resolves to Grade 1 or better, resume atezolizumab.b
 
• If event does not resolve to Grade 1 or better while withholding atezolizumab, permanently discontinue atezolizumab and contact Study Chair.c
 

Event	Management
Immune-mediated myocarditis, Grade 1 (CTCAE v4.0 guidelines only)	CTCAE v4.0 guidelines 
 
• Refer patient to cardiologist.
 
• Initiate treatment as per institutional guidelines.
 

Immune-mediated myocarditis, Grade 3-4	
 
• Permanently discontinue atezolizumab and contact Study Chair.c
 
• Refer patient to cardiologist.
 
• Initiate treatment as per institutional guidelines and consider antiarrhythmic drugs, temporary pacemaker, ECMO, or VAD as appropriate.
 
• Initiate treatment with corticosteroids equivalent to 1-2 mg/kg/day IV methylprednisolone and convert to 1-2 mg/kg/day oral prednisone or equivalent upon improvement.
 
• If event does not improve within 48 hours after initiating corticosteroids, consider adding an immunosuppressive agent.
 
• If event resolves to Grade 1 or better, taper corticosteroids over <math>\geq 1</math> month.
 

ECMO = extracorporeal membrane oxygenation; VAD = ventricular assist device.

a Atezolizumab may be withheld for longer period of time (i.e., >12 weeks after event onset) to allow for corticosteroids (if initiated) to be reduced to the equivalent of  $\leq 10$  mg/day oral prednisone. The acceptable length of the extended period of time must be agreed upon by the investigator and the Study Chair.

b If corticosteroids have been initiated, they must be tapered over  $\geq 1$  month to the equivalent of  $\leq 10$  mg/day oral prednisone before atezolizumab can be resumed.

c Resumption of atezolizumab may be considered in patients who are deriving benefit and have fully recovered from the immune-mediated event. Patients can be re-challenged with atezolizumab only after approval has been documented by both the investigator (or an appropriate delegate) and the Study Chair.

### 9.2.9 Infusion-related reactions and Cytokine-Release Syndrome

No premedication is indicated for the administration of Cycle 1 of atezolizumab. However, patients who experience an infusion-related reaction (IRR) or cytokine-release syndrome (CRS) with atezolizumab may receive premedication with antihistamines, antipyretics, and/or analgesics (e.g., acetaminophen) for subsequent infusions. Metamizole (dipyrone) is prohibited in treating atezolizumab-associated IRRs because of its potential for causing agranulocytosis.

IRRs are known to occur with the administration of monoclonal antibodies and have been reported with atezolizumab. These reactions, which are thought to be due to release of cytokines and/or other

chemical mediators, occur within 24 hours of atezolizumab administration and are generally mild to moderate in severity.

CRS is defined as a supraphysiologic response following administration of any immune therapy that results in activation or engagement of endogenous or infused T cells and/or other immune effector cells. Symptoms can be progressive, always include fever at the onset, and may include hypotension, capillary leak (hypoxia), and end-organ dysfunction (Lee et al. 2019). CRS has been well documented with chimeric antigen receptor T-cell therapies and bispecific T-cell engager antibody therapies but has also been reported with immunotherapies that target PD-1 or PD-L1 (Rotz et al. 2017; Adashek and Feldman 2019), including atezolizumab.

There may be significant overlap in signs and symptoms of IRRs and CRS, and in recognition of the challenges in clinically distinguishing between the two, consolidated guidelines for medical management of IRRs and CRS are provided in the table below.

### Management Guidelines for Infusion-Related Reactions and Cytokine-Release Syndrome

Event	Management
Grade 1 a Fever b with or without constitutional symptoms	
 
• Immediately interrupt infusion.
 
• Upon symptom resolution, wait for 30 minutes and then restart infusion at half the rate being given at the time of event onset.
 
• If the infusion is tolerated at the reduced rate for 30 minutes, the infusion rate may be increased to the original rate.
 
• If symptoms recur, discontinue infusion of this dose. Administer symptomatic treatment, c including maintenance of IV fluids for hydration.
 
• In case of rapid decline or prolonged CRS (> 2 days) or in patients with significant symptoms and/or comorbidities, consider managing as per Grade 2.
 
• For subsequent infusions, consider administration of oral premedication with antihistamines, anti-pyretics, and/or analgesics, and monitor closely for IRRs and/or CRS.
 

Grade 2 a Fever b with hypotension not requiring vasopressors and/or Hypoxia requiring low-flow oxygen d by nasal cannula or blow-by	
 
• Immediately interrupt infusion.
 
• Upon symptom resolution, wait for 30 minutes and then restart infusion at half the rate being given at the time of event onset.
 
• If symptoms recur, discontinue infusion of this dose.
 
• Administer symptomatic treatment. c
 
• For hypotension, administer IV fluid bolus as needed.
 
• Monitor cardiopulmonary and other organ function closely (in the ICU, if appropriate). Administer IV fluids as clinically indicated, and manage constitutional symptoms and organ toxicities as per institutional practice.
 

	
 
• Rule out other inflammatory conditions that can mimic CRS
 
• (e.g., sepsis). If no improvement within 24 hours, initiate workup and assess for signs and symptoms of HLH or MAS.
 
• Consider IV corticosteroids (e.g., methylprednisolone 2 mg/kg/day or dexamethasone 10 mg every 6 hours).
 
• Consider anti-cytokine therapy. e
 
• Consider hospitalization until complete resolution of symptoms. If no improvement within 24 hours, manage as per Grade 3, that is, hospitalize patient (monitoring in the ICU is recommended), permanently discontinue atezolizumab, and contact Study Chair.
 
• If symptoms resolve to Grade 1 or better for 3 consecutive days, the next dose of atezolizumab may be administered. For subsequent infusions, consider administration of oral premedication with antihistamines, anti-pyretics, and/or analgesics and monitor closely for IRRs and/or CRS.
 
• If symptoms do not resolve to Grade 1 or better for 3 consecutive days, contact Study Chair.
 

--	---

**Table. Management Guidelines for Infusion-Related Reactions and Cytokine-Release Syndrome (cont.)**

Event	Management
Grade 3 a Fever b with hypotension requiring a vasopressor (with or without vasopressin) and/or Hypoxia requiring	
 
• Permanently discontinue atezolizumab and contact Study Chair. f
 
• Administer symptomatic treatment. c
 
• For hypotension, administer IV fluid bolus and vasopressor as needed.
 
• Monitor cardiopulmonary and other organ function closely; monitoring in the ICU is recommended. Administer IV fluids as clinically indicated, and manage constitutional symptoms and organ toxicities
 

high-flow oxygen d          by nasal cannula,          face mask,          non-rebreather          mask, or venturi          mask
	
as per institutional practice.
 
 
• Rule out other inflammatory conditions that can mimic CRS (e.g., sepsis). If no improvement within 24 hours, initiate workup and assess for signs and symptoms of HLH or MAS.
 
• Administer IV corticosteroids (e.g., methylprednisolone 2 mg/kg/day or dexamethasone 10 mg every 6 hours).
 
• Consider anti-cytokine therapy. e
 
• Hospitalize patient until complete resolution of symptoms. If no improvement within 24 hours, manage as per Grade 4, that is, admit patient to ICU and initiate hemodynamic monitoring, mechanical ventilation, and/or IV fluids and vasopressors as needed; for patients who are refractory to anti-cytokine therapy, experimental treatments may be considered at the discretion of the investigator and in consultation with the Study Chair.
 


Grade 4 a          Fever b with          hypotension          requiring multiple          vasopressors          (excluding          vasopressin)  and/or          Hypoxia requiring          oxygen by positive          pressure (e.g.,          CPAP, BiPAP,          intubation and          mechanical          ventilation)
	
 
• Permanently discontinue atezolizumab and contact Study Chair. f
 
• Administer symptomatic treatment. c
 
• Admit patient to ICU and initiate hemodynamic monitoring, mechanical ventilation, and/or IV fluids and vasopressors as needed. Monitor other organ function closely. Manage
 
• constitutional symptoms and organ toxicities as per institutional practice.
 
• Rule out other inflammatory conditions that can mimic CRS
 
• (e.g., sepsis). If no improvement within 24 hours, initiate workup and assess for signs and symptoms of HLH or MAS.
 
• Administer IV corticosteroids (e.g., methylprednisolone 2 mg/kg/day or dexamethasone 10 mg every 6 hours).
 
• Consider anti-cytokine therapy. e For patients who are refractory to anti-cytokine therapy, experimental treatments g may be considered at the discretion of the investigator and in consultation with the Study Chair
 
• Hospitalize patient until complete resolution of symptoms
 

ASTCT =American Society for Transplantation and Cellular Therapy; BiPAP =bi-level positive airway pressure; CAR =chimeric antigen receptor; CPAP =continuous positive airway pressure; CRS =cytokine-release syndrome; CTCAE =Common Terminology Criteria for Adverse Events; eCRF =electronic Case Report Form; HLH =hemophagocytic lymphohistiocytosis; ICU =intensive care unit; IRR =infusion-related reaction; MAS =macrophage activation syndrome; NCCN =National Cancer Comprehensive Network; NCI =National Cancer Institute.

Note: The management guidelines have been adapted from NCCN guidelines for management of CAR T-cell-related toxicities (Version 2.2019).

- a** Grading system for management guidelines is based on ASTCT consensus grading for CRS. NCI CTCAE (version as specified in the protocol) should be used when reporting severity of IRRs, CRS, or organ toxicities associated with CRS on the Adverse Event eCRF. Organ toxicities associated with CRS should not influence overall CRS grading.
- b** Fever is defined as temperature  $\geq 38^{\circ}\text{C}$  not attributable to any other cause. In patients who develop CRS and then receive anti-pyretic, anti-cytokine, or corticosteroid therapy, fever is no longer required when subsequently determining event severity (grade). In this case, the grade is driven by the presence of hypotension and/or hypoxia.
- c** Symptomatic treatment may include oral or IV antihistamines, anti-pyretics, analgesics, bronchodilators, and/or oxygen. For bronchospasm, urticaria, or dyspnea, additional treatment may be administered as per institutional practice.
- d** Low flow is defined as oxygen delivered at  $\leq 6$  L/min, and high flow is defined as oxygen delivered at  $> 6$  L/min.
- e** There are case reports where anti-cytokine therapy has been used for treatment of CRS with immune checkpoint inhibitors (Rotz et al. 2017; Adashek and Feldman 2019), but data are limited, and the role of such treatment in the setting of antibody-associated CRS has not been established.
- f** Resumption of atezolizumab may be considered in patients who are deriving benefit and have fully recovered from the event. Patients can be re-challenged with atezolizumab only after approval has been documented by both the investigator (or an appropriate delegate) and the Study Chair. For subsequent infusions, administer oral premedication with antihistamines, anti-pyretics, and/or analgesics, and monitor closely for IRRs and/or CRS. Premedication with corticosteroids and extending the infusion time may also be considered after consulting the Study Chair and considering the benefit-risk ratio.
- g** Refer to Riegler et al. (2019) for information on experimental treatments for CRS.

### 9.2.10 Neurologic Disorders

Myasthenia gravis and Guillain-Barré syndrome have been observed with single-agent atezolizumab. Patients may present with signs and symptoms of sensory and/or motor neuropathy. Diagnostic workup is essential for an accurate characterization to differentiate between alternative etiologies. Management guidelines for neurologic disorders are provided below.

### Management Guidelines for Neurologic Disorders

Event	Management
Immune-mediated neuropathy, Grade 1	
 
• Continue atezolizumab.
 
• Investigate etiology.
 

Immune-mediated neuropathy, Grade 2	
 
• Withhold atezolizumab for up to 12 weeks after event onset.a
 
• Investigate etiology.
 
• Initiate treatment as per institutional guidelines.
 
• If event resolves to Grade 1 or better, resume atezolizumab.b
 
• If event does not resolve to Grade 1 or better while withholding atezolizumab, permanently discontinue atezolizumab and contact Study Chair.
 

Immune-mediated neuropathy, Grade 3 or 4	
 
• Permanently discontinue atezolizumab and contact Study Chair.c
 
• Initiate treatment as per institutional guidelines.
 

Myasthenia gravis and Guillain-Barré syndrome (any grade)	
 
• Permanently discontinue atezolizumab and contact Study Chair.c
 
• Refer patient to neurologist.
 
• Initiate treatment as per institutional guidelines.
 
• Consider initiation of corticosteroids equivalent to 1-2 mg/kg/day oral or IV prednisone.
 

a Atezolizumab may be withheld for longer period of time (i.e., >12 weeks after event onset) to allow for corticosteroids (if initiated) to be reduced to the equivalent of  $\leq 10$  mg/day oral prednisone. The acceptable length of the extended period of time must be agreed upon by the investigator and the Study Chair.

b If corticosteroids have been initiated, they must be tapered over  $\geq 1$  month to the equivalent of  $\leq 10$  mg/day oral prednisone before atezolizumab can be resumed.

c Resumption of atezolizumab may be considered in patients who are deriving benefit and have fully recovered from the immune-mediated event. Patients can be re-challenged with atezolizumab only after approval has been documented by both the investigator (or an appropriate delegate) and the Study Chair.

#### 9.2.11 Immune-mediated Meningoencephalitis

Immune-related meningoencephalitis is an identified risk associated with the administration of atezolizumab. Immune-mediated meningoencephalitis should be suspected in any patient presenting with signs or symptoms suggestive of meningitis or encephalitis, including, but not limited to, headache, neck pain, confusion, seizure, motor or sensory dysfunction, and altered or depressed level of consciousness.

Encephalopathy from metabolic or electrolyte imbalances needs to be distinguished from potential meningoencephalitis resulting from infection (bacterial, viral, or fungal) or progression of malignancy, or secondary to a paraneoplastic process.

All patients being considered for meningoencephalitis should be urgently evaluated with a CT scan and/or MRI scan of the brain to evaluate for metastasis, inflammation, or edema. If deemed safe by the treating physician, a lumbar puncture should be performed and a neurologist should be consulted.

Patients with signs and symptoms of meningoencephalitis, in the absence of an identified alternate etiology, should be treated according to the guidelines below.

### Management Guidelines for Immune-Mediated Meningoencephalitis

Event	Management
Immune-mediated meningoencephalitis, all grades	
 
● Permanently discontinue atezolizumab and contact Study Chair.
 
● Refer patient to neurologist.
 
● Initiate treatment with corticosteroids equivalent to 1-2 mg/kg/day IV methylprednisolone and convert to 1-2 mg/kg/day oral prednisone or equivalent upon improvement.
 
● If event does not improve within 48 hours after initiating corticosteroids, consider adding an immunosuppressive agent.
 
● If event resolves to Grade 1 or better, taper corticosteroids over <math>\geq 1</math> month.
 

a Resumption of atezolizumab may be considered in patients who are deriving benefit and have fully recovered from the immune-mediated event. Patients can be re-challenged with atezolizumab only after approval has been documented by both investigator (or an appropriate delegate) and the Study Chair.

#### 9.2.12 Immune-Mediated Myositis

Immune-mediated myositis has been associated with the administration of atezolizumab. Myositis or inflammatory myopathies are a group of disorders sharing the common feature of inflammatory muscle injury; dermatomyositis and polymyositis are amongst the most common disorders. Initial diagnosis is based on clinical (muscle weakness, muscle pain, skin rash in dermatomyositis), biochemical (serum creatine-kinase increase), and imaging (electromyography/MRI) features, and is confirmed with a muscle-biopsy. Patients with signs and symptoms of myositis, in the absence of an identified alternate etiology, should be treated according to the guidelines below.

### Management guidelines for Immune-Mediated Myositis

Event	Management
Immune-mediated myositis, Grade 1	
 
• Continue atezolizumab
 
• Refer patient to rheumatologist or neurologist.
 
• Initiate treatment as per institutional guidelines
 

Immune-mediated myositis, Grade 2	
 
• Withhold atezolizumab for up to 12 weeks after event onseta and contact Study Chair.
 
• Refer patient to rheumatologist or neurologist.
 
• Initiate treatment as per institutional guidelines .
 
• Consider treatment with corticosteroid equivalent to 1-2 mg/kg/day IV methylprednisolone and convert to 1-2 mg/kg/day oral prednisone or equivalent upon improvement.
 
• If corticosteroids are initiated and event does not improve within 48 hours after initiating corticosteroids, consider adding an immunosuppressive agent.
 
• If event resolves to Grade 1 or better, resume atezolizumab.b
 
• If event does not resolve to Grade 1 or better while withholding atezolizumab, permanently discontinue atezolizumab and contact Study Chair.
 

Immune-mediated myositis, Grade 3	
 
• Withhold atezolizumab for up to 12 weeks after event onseta and contact Study Chair.
 
• Refer patient to rheumatologist or neurologist.
 
• Initiate treatment as per institutional guidelines .
 
• Respiratory support may be required in more severe cases .
 
• Initiate treatment with corticosteroids equivalent to 1-2 mg/kg/day IV methylprednisolone or higher-dose bolus if patient is severely compromised (e.g. cardiac or respiratory symptoms, dysphagia, or weakness that severely limits mobility); convert to 1-2 mg/kg/day oral prednisolone or equivalent upon improvement.
 
• If event does not improve within 48 hours after initiating corticosteroids, consider adding an immunosuppressive agent.
 
• If event resolves to Grade 1 or better, resume atezolizumab.b
 
• If event does not resolve to Grade 1 or better while withholding atezolizumab, permanently discontinue atezolizumab and contact Study Chair.c
 
• For recurrent events, treat as a Grade 4 event.
 

Event	Management
Immune-mediated myositis, Grade 4	
 
• Permanently discontinue atezolizumab and contact Study Chair.c
 
• Refer patient to rheumatologist or neurologist.
 
• Initiate treatment as per institutional guidelines. Respiratory support may be required in more severe cases.
 
• Initiate treatment with corticosteroids equivalent to 1-2 mg/kg/day IV methylprednisolone or higher-dose bolus if patient is severely compromised (e.g. cardiac or respiratory symptoms, dysphagia, or weakness that severely limiting mobility); convert to 1-2 mg/kg/day oral prednisone or equivalent upon improvement.
 
• If event does not improve within 48 hours after initiating corticosteroids, consider adding an immunosuppressive agent.
 
• If event resolves to Grade 1 or better, taper corticosteroids over <math>\geq 1</math> month.
 

a Atezolizumab may be withheld for longer period of time (i.e., >12 weeks after event onset) to allow for corticosteroids (if initiated) to be reduced to the equivalent of  $\leq 10$  mg/day oral prednisone. The acceptable length of the extended period of time must be agreed upon by the investigator and the Study Chair.

b If corticosteroids have been initiated, they must be tapered over  $\geq 1$  month to the equivalent of  $\leq 10$  mg/day oral prednisone before atezolizumab can be resumed.

c Resumption of atezolizumab may be considered in patients who are deriving benefit and have fully recovered from the immune-mediated event. Patients can be re-challenged with atezolizumab only after approval has been documented by both the investigator (or an appropriate delegate) and the Study Chair.

### **Management guidelines for SCARs**

- For suspected SCARs the patients should be referred to a dermatologist for further diagnosis and management
- Atezolizumab should be withheld for patients with suspected SJS or TEN
- Atezolizumab should be permanently withdrawn for any grade confirmed SJS or TEN
- Caution should be used when considering the use of atezolizumab in a patient who has previously experienced a severe or life-threatening skin adverse reaction on prior treatment with other immune-stimulatory anticancer agents

#### 9.2.14 Overdose

In clinical trials with atezolizumab, doses of up to 20 mg/kg have been administered. The standard fixed dose of 1200 mg is equivalent to 15 mg/kg in a typical patient. No dose-limiting toxicities were observed at the 20 mg/kg dose level and the incidence and intensity of AEs reported have not been shown to be dependent on dose. A maximum tolerated dose has not been established.

Atezolizumab is supplied in vials containing the fixed 1200 mg dose of drug substance, which minimizes the chance of overdose. Because the dose per patient is not based on weight or body surface area, and no dose calculation is required, the risk of overdose due to medication errors is minimal.

The data available to date suggest that the potential for harm from overdose is very low.

### 9.3 Anticipated Toxicities of Carboplatin and Dose Modifications

Carboplatin is known to cause bone marrow suppression including myelosuppression, anemia, and thrombocytopenia. Carboplatin-based chemotherapy is considered to be moderately emetogenic. Patients will be monitored for carboplatin-related adverse events.

#### 9.3.1 Hematologic Toxicity

**At the start of each cycle if the patient is receiving carboplatin, the ANC must be  $\geq 1000/\text{mm}^3$  and the platelet count must be  $\geq 80,000/\text{mm}^3$ .** Platelets must be  $\geq 100,000$  for study entry. Growth factors may be used in accordance with American Society of Clinical Oncology (ASCO) and National Comprehensive Cancer Network (NCCN) guidelines (Smith et al. 2006; NCCN 2012). Upon recovery, dose adjustments at the start of a subsequent cycle will be made on the basis of the lowest platelet and neutrophil values from the previous cycle (see Table below).

##### 9.3.1.1 Carboplatin Dose Modification for Hematologic Toxicities

Toxicity	Carboplatin Dose
ANC $< 500/\text{mm}^3$ and platelets $\geq 50,000/\text{mm}^3$	Decrease AUC by 1
Platelets $< 50,000/\text{mm}^3$ , regardless of ANC	Decrease AUC by 1
Platelets $< 50,000/\text{mm}^3$ with Grade $\geq 2$ bleeding, regardless of ANC	Decrease AUC by 2
ANC $< 1000/\text{mm}^3$ plus fever of $\geq 38.5^\circ\text{C}$	Decrease AUC by 1

All dose reductions for the first episode of neutropenic fever or thrombocytopenia (platelet count  $< 25,000$  or  $< 50,000$  with bleeding or that requires transfusion) are permanent. If a second episode of neutropenic fever or thrombocytopenia requiring dose reduction occurs, the dose of carboplatin will be reduced according to physician judgment and local standard practice. Colony-stimulating factors, such as granulocyte colony-stimulating factor, may be used instead of dose reduction for neutropenic fever or Grade 4 neutropenia, according to the local standard practice and ASCO guideline. Patients who require a third dose reduction will immediately discontinue chemotherapy.

In the event that dose adjustments are needed for both ANC and platelets, patients are to receive the lower dose.

**For Grade 3 ANC toxicity** (ANC  $< 1000-500/\text{ml}$ ), carboplatin should be withheld until the patient recovers completely or to Grade 1 toxicity. The treatment should then be resumed at 50% dose (permanent dose reduction). If recovery to Grade 1 toxicity does not occur within 3 weeks, the patient's chemotherapy will be discontinued.

Treatment with carboplatin can be delayed for up to 3 weeks until the Day 1 ANC is  $\geq 1000/\text{mm}^3$  and the platelet count is  $\geq 80,000/\text{mm}^3$ . However, if the counts have not recovered in 3 weeks, the patient's chemotherapy will be dose-reduced, held until adequate neutrophil recovery, or

discontinued, according to physician judgment and local standard practice. If chemotherapy is held longer than 42 days, all study treatment should be discontinued.

Investigators should be vigilant and alert to early and overt signs of myelosuppression, infection, or febrile neutropenia so that these complications can be promptly and appropriately managed. Patients should be made aware of these signs and encouraged to seek medical attention at the earliest opportunity. If chemotherapy must be withheld because of hematologic toxicity, full blood counts (including differential WBC) should be obtained weekly until the counts reach the lower limits for treatment as outlined. The treatment schedule will then proceed in the usual sequence.

No dose reductions will be made for anemia. Patients should be supported per the treating physician’s institution’s guidelines.

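### Section 9.3.1.1 gives conflicting neutrophil rules: withheld Grade 3 ANC is resumed at a permanent 50% carboplatin dose, while ANC below 500 loses only one AUC unit or gets G-CSF instead

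*Combined protocol and SAP*

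**What the plan says.** Both arms start carboplatin at AUC 6 (protocol section 8.1). Section 9.3.1 requires a Day 1 ANC of at least 1000/mm³. It says that, after recovery, dose changes "will be made on the basis of the lowest platelet and neutrophil values from the previous cycle", and refers to the table in 9.3.1.1.

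In that table, ANC below 500 with platelets of at least 50,000 carries "Decrease AUC by 1", and so does ANC below 1000 with fever. Colony-stimulating factors "may be used instead of dose reduction for neutropenic fever or Grade 4 neutropenia". The sentence that makes cuts permanent has as its subject "All dose reductions for the first episode of neutropenic fever or thrombocytopenia"; it does not name afebrile ANC below 500. A later sentence adds: "Patients who require a third dose reduction will immediately discontinue chemotherapy".

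A separate paragraph covers Grade 3 ANC, defined there as 500 to 1000. It says "carboplatin should be withheld until the patient recovers completely or to Grade 1 toxicity", and then "The treatment should then be resumed at 50% dose (permanent dose reduction". "If recovery to Grade 1 toxicity does not occur within 3 weeks", chemotherapy stops. The paragraph after it allows a delay of up to 3 weeks for Day 1 ANC to reach 1000. After that it leaves reducing, holding or stopping to the physician, with all study treatment ending after a 42-day hold.

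In 9.3.2.1 the table gives AUC minus 1 for Grade 3 or 4 nausea/vomiting and for Grade 3 or 4 oral mucositis. The text below it gives a reversible 25% cut for nausea/vomiting and a permanent 75% dose for Grade 3 mucositis.

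**The concern.** A dose-reduction scheme normally cuts at least as much for the worse grade as for the milder one. Here the paragraph for the milder grade halves the dose permanently and offers no G-CSF alternative, while the row for the worse grade takes off one AUC unit and does offer one. Carboplatin is the whole of the control treatment and the backbone of the combination arm. Section 9.3 lists myelosuppression among its expected effects. A site that follows the Grade 3 paragraph and a site that follows the table logic would give clearly different doses for the same blood count. What is at stake is dose intensity and consistency across sites, not the sample size or the analysis.

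**Working it through.** **Inputs.** Starting dose AUC 6 (section 8.1). Maximum doses 900, 750 and 600 mg at AUC 6, 5 and 4 (section 10.2). Cuts from 9.3.1.1 and 9.3.2.1. I take the 50% to be half of the dose in use before the hold.

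**Reproducing the plan's doses.** Maximum dose = AUC × 150 mg, where 150 is the GFR cap of 125 plus the 25 that the stated multiplier implies: 6 × 150 = 900, 5 × 150 = 750, 4 × 150 = 600. All three match.

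**Size of each cut.** AUC minus 1 removes 1/AUC of the dose; the Grade 3 paragraph removes 0.5.

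| Dose before the event | Grade 3 ANC, withheld | ANC below 500 | Ratio of cuts |
|---|---|---|---|
| AUC 6 (900 mg) | AUC 3, 450 mg, 50% | AUC 5, 750 mg, 1/6 = 16.7%, or 0% with G-CSF | 0.5 × 6 = 3.0 |
| AUC 5 (750 mg) | AUC 2.5, 375 mg, 50% | AUC 4, 600 mg, 1/5 = 20%, or 0% with G-CSF | 0.5 × 5 = 2.5 |

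The largest row in the table (platelets below 50,000 with Grade 2 or worse bleeding) is AUC minus 2: 2/6 = 33.3% from AUC 6, leaving 600 mg. At the starting dose the Grade 3 ANC cut therefore exceeds every row. The percentages do not depend on renal function. At GFR 90, for example, the start is 6 × 115 = 690 mg, and the two rules give 345 and 575 mg.

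**Which patients the 50% paragraph covers.** There are three ways to read it.
- *Low count on the dosing day.* The references to withholding and resuming point this way, and 9.3.1 bases dose changes on the previous cycle's lowest counts. A dosing-day ANC below 500 is then outside the paragraph, so the milder count gets the larger cut.
- *Any Grade 3 ANC.* The inversion then reaches more patients, because the table has no afebrile row for 500 to 1000.
- *An ANC below 500 that climbs through 500 to 1000 during the hold also counts.* The same patient then meets AUC minus 1 (or G-CSF) and the permanent 50% dose. The lower-dose tie-break in 9.3.1.1 is for ANC against platelets, not for two ANC rules.

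**Restart threshold and 3-week outcome.** The Grade 3 paragraph waits for Grade 1 or better and stops chemotherapy if this is not reached in 3 weeks. The next paragraph restarts at ANC 1000 and uses judgment after 3 weeks. Grade 3 ends at 1000 and Grade 2 lies between it and Grade 1, so a patient just above 1000 may restart under one paragraph and not under the other. At 3 weeks the same patient could be taken off chemotherapy or treated.

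**Section 9.3.2.1.** From AUC 6 the table gives 750 mg and the text 0.75 × 900 = 675 mg, a gap of 75 mg or 25 − 16.7 = 8.3 percentage points. From AUC 5 it is 600 against 562.5 mg, or 5 points. The 75% sentence names Grade 3 mucositis only, so Grade 4 is left with the table row, which is the smaller cut at both doses.

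**The case against.** The best case against has five parts.

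First, a low count on the dosing day is a failure to recover, whereas the table deals with the depth of a nadir that did recover. The ratio of 3.0 therefore partly compares different events. That stands as a caution: a reader might infer a proven inversion on every reading, and the text does not settle that. Under the third reading above, the fault is two rules for one patient. It is still a contradiction.

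Second, a reader might extend the comparison to AUC 4 (50% against 25%). The documents do not support this in general. A patient who reached AUC 4 by two one-unit cuts would be at a third reduction and would stop chemotherapy. The comparison exists only after a single AUC-minus-2 step, so I leave it out.

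Third, a reader might call the 50% cut needless under-dosing. Nothing in the documents shows that AUC 5 is enough after delayed neutrophil recovery. That is for the study's clinicians.

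Fourth, the rules are worded as guidance and there are outlets. Section 9.4 lets the investigator reduce for any grade, so too small a cut after ANC below 500 is never forced. Section 9.3.1 allows growth factors under published guidelines without restricting them by grade, and section 8.2.1 allows prophylactic pegfilgrastim. These soften the problem. However, the 9.4 freedom is to reduce. A milder cut than 50% is a modification to be taken to the Principal Investigator in advance, and the growth-factor sentence does not waive the 50% cut. The 9.4 allowance to keep the same dose gives alopecia and altered taste as examples, not neutropenia.

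Fifth, the 9.3.2.1 gaps are small, and a footnote to that table refers to the treating physician's judgment. True, but the footnote does not say whether the table or the text governs.

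**Conclusion.** The concern holds as a conflict in the written dosing rules, and one that should be fixed. Read literally, 9.3.1.1 cuts carboplatin by 50%, permanently, for Grade 3 ANC that holds up dosing, and by 16.7% (or not at all, with G-CSF) for ANC below 500, from the AUC 6 start. From AUC 5 the figures are 50% and 20%. The milligram figures assume the capped dose; the percentages do not. The conflicts over restart threshold, 3-week outcome, nausea/vomiting and mucositis are also in the text, but smaller.

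A reader might infer that the rules bias the comparison or cost power. The documents do not support this: both arms use the same rules, and nothing in the sample-size section depends on them. No neutropenia rates are given, and permitted pegfilgrastim may make the event less frequent, so the effect on PFS cannot be sized.

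**What to change.** - **Grade 3 ANC.** Delete the 50% sentence in 9.3.1.1, or replace it with a cut no larger than AUC minus 1, with the same G-CSF option as Grade 4. From AUC 6 the resumed dose would then be at least AUC 5 (750 mg at the cap, 83.3% of the start) instead of AUC 3.
- **Restart and 3-week rule.** Keep one ANC threshold and one outcome. One choice already in the section is Day 1 ANC of at least 1000, then the judgment rule with the 42-day limit.
- **Section 9.3.2.1.** Keep either the table rows or the 25% and 75% sentences. If the sentences stay, extend the 75% dose to Grade 4 mucositis so that it is not cut less than Grade 3.
- **Patients already dosed.** Record which rule was applied to each.

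The study's clinicians should confirm which rule stays in each case. The cost is a protocol clarification or amendment to a few named sentences; sample size and analysis do not change.
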